8.10. Severe adverse events (SAEs)

The following have been identified as reportable SAEs:

Newborns

- Newborn death
- Admission to a Level-2 or above newborn care unit

During the postnatal stay of the mother-newborn dyad, newborns will be under round-the-clock monitoring of the hospital team. Newborn deaths and admission to neonatal intensive care will be notified to the study team, and documented using the SAE forms. During post-discharge follow-up, SAEs will be documented by study evaluation workers on visit days based on information and records provided by the family.

Upon identification of an SAE, it will be verified and notified within 24 hours by the Principal Investigator to the data and safety monitoring board (DSMB). All SAEs will also be communicated to the ethics committee on a monthly basis.

A masked interim analysis will be performed by the DSMB to review the safety of the trial once 50% of participants have completed the follow-up, where relative incidence rates and severity of events in the two arms will be compared.

Due to the low-risk nature of the study, no stopping rules have been defined.

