Post 48 hours, the mother-baby dyad will be discharged from the facility in ambulatory KMC (provided there are no signs of complications in either mother or baby that require a longer duration of hospital stay). The KMC team will ensure that the mother-baby dyad is discharged in the KMC position along with counselling on continuing KMC similarly for at least 1 more day at home. The KMC team will remind mothers/ family members telephonically in the morning and afternoon of the day after discharge to encourage the provision of prolonged KMC (ideally >=20 hours, but at least >=8 hours). Post 72 hours, on Day 4, the KMC team will make a final call to mothers and family members to recommend them to continue keeping the baby in SSC for as long as they wish, as per their desire and comfort, and be advised to continue to breastfeed in the KMC position throughout the newborn period.

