8.8.2. Secondary outcome measures

	Secondary Outcome Measures
Outcome 1: Exclusive Breastfeeding at day 28 of birth.	Description: Exclusive breastfeeding is defined as feeding an infant with only breast milk and no additional food, water, or other liquids (with the exception of medicines and vitamins, if needed). This will be assessed on Day 29 follow up visit using 24 hour dietary recall method for exclusive breastfeeding. Exclusive breastfeeding will be measured in a manner consistent with the Infant and Young Child Feeding indicators recommended by WHO and UNICEF.
Outcome 2: Score on the Breastfeeding Experience	Description: The Breastfeeding Experience Scale is a 19-point scale of potential negative experiences that the mother may have had

Scale as reported by mother on follow-up day 8 to assess early challenges with breastfeeding.	since birth (e.g., sore nipples and other breast-related problems, infant-related challenges to breastfeeding success, mother's own perceptions and anxiety, etc.), and the degree to which those experiences posed a challenge to breastfeeding.
	We will aim to compare both the score on the number of negative experiences as well as the degree to which these experiences influenced breastfeeding between the intervention and control groups.
Outcome 3: Possible Serious Bacterial Infection (PSBI) among infants on follow-up days (days 4, 8, 15 and 29).	 Description: Possible serious bacterial infection commonly known as PSBI is defined as the presence of any of the following clinical signs in the infants: Convulsions Not able to feed at all No movement at all Low body temperature (< 35.5°C) Not feeding well Movement only when stimulated Severe chest indrawing High body temperature (38°C or above) Fast breathing (60 breaths per minute or more) in infants < 7 days The PSBI signs will be assessed by trained and standardised workers during follow-up visits as per IMNCI assessment protocol on days 4, 8, 15 and 29.
Outcome 4: Maternal	Description:
depression measured at 15days after birth.	 The Edinburgh Postnatal Depression Scale (EPDS) The scale consists of 10 short statements. Responses are scored 0, 1, 2 and 3 based on likert scale. Items 3, 5 to 10 are reverse scored (i.e., 3, 2, 1, and 0). The total score is calculated by adding together the scores for each of the 10 items. Mothers scoring above 13 will be considered as suffering from depression. The EPDS will be administered by trained and standardised workers

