8.11. Data collection

Infants will be followed up on days 1 (24 hours after birth), 2 (48 hours after birth), 4, 8, 15 and 29 for various outcomes, including vital status, weight, infant feeding practices (observation and 24-hr recall questionnaire), other care practices (24-hour recall questionnaire), etc. The IOA team responsible for conducting the data collection will be masked to the study group. There will be a pair of assessors – a male and female assessor, conducting each follow-up visit. This is because

some of the assessments, such as breastfeeding observation and maternal mental health are sensitive and require a female assessor. The male assessors have been included for logistical reasons and will focus on gender-neutral measures like anthropometry, PSBI assessment, socioeconomic status.

STUDY PERIOD									
	Screening		F	Close -out					
Timepoint	Labor	<4hr	D1	D2	D4	D8	D15	D29	
SCREENING:									
Verbal Consent & Registration	х								
Eligibility Screening		х							
Informed Written Consent		х							
Randomization & Enrolment		х							
INTERVENTION:									
Skin-to-skin contact log			х	х					
OUTCOME ASSESSMENT:									
A. Newborn weight		х	х	х	х	х	х	х	
B. PSBI Module					х	х	х	х	
C. Anthropometry Measurement (length, head circumference, MUAC)			х					х	
D. Breastfeeding Observation (BBAT)				-		х			
E. Feeding Module			х	х	х	х	х	х	
F. Newborn Care Practices (SSC)			х	х	х	х	х	х	
G. Maternal history					х				
H. Breastfeeding Experience Scale						х			
I. Maternal Depression							х		

J. Mother-infant bonding					х
K. Breastfeeding Self-Efficacy					х
L. Socio Economic Status				х	
Mechanistic sub-study* (continuous temperature + plethysmography)		~	^		

* Sub-sample of 40 infants each from intervention and control groups (Mechanistic cohort)

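### The SAE list in 8.10 does not make reportable an infant's admission after discharge to a ward that is not a Level-2 or above newborn unit

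*Protocol*

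**What the plan says.** Protocol 8.10 introduces the reportable SAEs as a list and gives two, both in the newborn: death, and "Admission to a Level-2 or above newborn care unit". Once an SAE is identified, "it will be verified and notified within 24 hours by the Principal Investigator" to the DSMB. All SAEs also go to the ethics committee monthly. After discharge, "SAEs will be documented by study evaluation workers on visit days based on information and records provided by the family".

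At 50% of follow-up the DSMB carries out a safety review in which "relative incidence rates and severity of events in the two arms will be compared". The same section says that "no stopping rules have been defined", because the study is considered low risk.

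Four other places bear on the point:

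- **8.6 (Intervention):** "Post 48 hours, the mother-baby dyad will be discharged from the facility in ambulatory KMC", provided that neither mother nor baby has signs of complications.
- **8.8.2, Outcome 3 (PSBI):** clinical signs are assessed "during follow-up visits as per IMNCI assessment protocol on days 4, 8, 15 and 29".
- **8.11 (Data collection):** infants are followed "for various outcomes, including vital status, weight, infant feeding practices" and care practices. The list is left open at its end.
- **8.15 and 8.16.3:** the DSMB monitors the trial on a continuing basis, and its safety review includes SAE incidence. Adverse events of any kind are to be monitored and documented.

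**The concern.** The only admission on the list is defined by the type of unit that receives the infant. How ill the infant is, and whether inpatient care was needed, do not enter. During the birth stay this does little harm, since a sick newborn in a study facility would be expected to go to its newborn unit. After discharge the infant is at home, and the protocol does not say where infants who fall ill at home are admitted. Two infants with the same illness could be classified differently because one went to a newborn unit and the other to a paediatric ward.

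What is at stake is safety reporting. The trial has no stopping rules and one planned comparison of events by arm. An admission that is not an SAE triggers no expedited notice, and it reaches that comparison only if it is recorded by some means that the protocol does not describe.

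**Working it through.** No figure in the protocol bears on this point, so the check is a reading of the text. Take an infant sent home well at 48 hours, admitted to a general paediatric ward after the day-15 visit, and back home and recovered before the day-29 visit.

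1. **SAE list (8.10).** The infant did not die and was not in a listed unit. The event is not an SAE.
2. **Capture after discharge (8.10).** Evaluation workers document SAEs from family information and records. This route is retrospective and could pick the admission up, but as written it covers SAEs only, so it has the same limit as step 1.
3. **Notification (8.10).** The 24-hour notice and the monthly ethics report follow from an SAE. Neither applies.
4. **Outcomes (8.8).** The three primary outcomes are early weight change, weight gain velocity and the BBAT score. The six secondary outcomes are exclusive breastfeeding, breastfeeding experience, PSBI, maternal depression, bonding and self-efficacy. The sub-study adds hypothermia and heart rate variability. None is hospital admission.
5. **Visit modules A to L (8.11).** Weight, PSBI, anthropometry, BBAT, feeding, care practices, maternal history, breastfeeding experience, depression, bonding, self-efficacy and socioeconomic status. None names an admission. The feeding and care-practice questionnaires use 24-hour recall, so they would not reach back to this event. Vital status covers death only.
6. **PSBI as a substitute (8.8.2).** Signs are looked for at the visit. This infant can be negative on day 15 and again on day 29.
7. **General safety text (8.11, 8.15, 8.16.3).** The open-ended visit list, the DSMB's ongoing remit and the promise to document adverse events leave room for the admission to be recorded. None of them names it, makes it reportable or says how it reaches the DSMB.

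The visit timing gives some context. Section 8.8.1 equates day 8 with 7 completed days. Assuming the same convention for the other visits after discharge, they fall at 3, 7, 14 and 28 completed days, with discharge at 2.

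- Time from discharge to the last visit: 28 − 2 = 26 days, and 26/28 = 92.9%.
- Intervals: 3 − 2 = 1, 7 − 3 = 4, 14 − 7 = 7, 28 − 14 = 14. They sum to 26, and the longest is 14/26 = 53.8% of it.
- Time after the 72-hour intervention period: 28 − 3 = 25 of the 26 days.

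The first figure is time at home, and the second is visit spacing, which matters only for PSBI signs. Neither measures how many admissions are missed.

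**The case against.** The strongest case against is that the list is a deliberate choice in a low-risk trial and may leave out nothing of consequence. All infants are neonates throughout follow-up, and admission to a listed unit counts both before and after discharge. If sick neonates in this catchment all go to such units, the gap is empty. The most intensive part of the intervention is also the best covered: the first 48 hours are spent under round-the-clock hospital monitoring, and 25 of the 26 days at home fall after the 72-hour period. Detail on forms may sit in the manual of operations or case record forms, which are not shown.

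Much of this stands, and it limits the size of the point. It does not alter what 8.10 makes reportable.

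Three stronger readings are tempting, and the protocol does not support them:

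- **That the DSMB cannot see these admissions, or that oversight consists only of SAE notices and the 50% review.** Section 8.15 gives the DSMB a continuing safety remit that includes SAE incidence without being confined to it. The 50% review in 8.10 refers to events in general.
- **That 93% of follow-up is unprotected.** Deaths and admissions to listed units remain reportable on every one of those days.
- **That 8.10 contradicts 8.16.3.** A promise to document adverse events does not say that each one is an SAE. The two texts differ in breadth, but they do not conflict.

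**Conclusion.** The point holds as a narrow gap in safety reporting. Followed as written, 8.10 leaves an infant's post-discharge admission to any ward other than a listed newborn unit outside SAE reporting, and nothing else in the protocol names it. General wording permits recording but does not require it, so inclusion in the by-arm comparison is not assured.

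The size is unknown. The protocol gives no admission rate and no referral pathway, so the number could be small or zero. The conclusion rests on one factual assumption: that at least some infants who fall ill at home may be admitted to such wards. No primary or secondary estimate and no sample size figure is affected. Severity is low. The point is worth raising because the remedy costs little and what counts as reportable is fixed in the protocol itself.

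**What to change.** Keep both existing items in 8.10 and add a third: *any other inpatient hospital admission of the infant after discharge from the birth stay, up to the day-29 visit, whatever the unit.* Record the unit type and level on the SAE form, so that admissions to Level-2 or above units can still be shown separately. Have evaluation workers ask, on days 4, 8, 15 and 29, about any admission since the last visit.

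Add to the list and replace nothing. A single item for any inpatient admission that excluded the birth stay would make it arguable whether a transfer to the SNCU or NICU during that stay still counts.

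The cost is one line in 8.10, one field on the SAE form and one question at four visits that already take place. Family report and records are already the stated source, so no new team or visit is needed. The downside is a modest increase in SAE reports.

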8.11. Data collection

Infants will be followed up on days 1 (24 hours after birth), 2 (48 hours after birth), 4, 8, 15 and 29 for various outcomes, including vital status, weight, infant feeding practices (observation and 24-hr recall questionnaire), other care practices (24-hour recall questionnaire), etc. The IOA team responsible for conducting the data collection will be masked to the study group. There will be a pair of assessors – a male and female assessor, conducting each follow-up visit. This is because

some of the assessments, such as breastfeeding observation and maternal mental health are sensitive and require a female assessor. The male assessors have been included for logistical reasons and will focus on gender-neutral measures like anthropometry, PSBI assessment, socioeconomic status.

STUDY PERIOD									
	Screening		F	Close -out					
Timepoint	Labor	<4hr	D1	D2	D4	D8	D15	D29	
SCREENING:									
Verbal Consent & Registration	х								
Eligibility Screening		х							
Informed Written Consent		х							
Randomization & Enrolment		х							
INTERVENTION:									
Skin-to-skin contact log			х	х					
OUTCOME ASSESSMENT:									
A. Newborn weight		х	х	х	х	х	х	х	
B. PSBI Module					х	х	х	х	
C. Anthropometry Measurement (length, head circumference, MUAC)			х					х	
D. Breastfeeding Observation (BBAT)				-		х			
E. Feeding Module			х	х	х	х	х	х	
F. Newborn Care Practices (SSC)			х	х	х	х	х	х	
G. Maternal history					х				
H. Breastfeeding Experience Scale						х			
I. Maternal Depression							х		

J. Mother-infant bonding					х
K. Breastfeeding Self-Efficacy					х
L. Socio Economic Status				х	
Mechanistic sub-study* (continuous temperature + plethysmography)		~	^		

* Sub-sample of 40 infants each from intervention and control groups (Mechanistic cohort)

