8.2. Study setting

The multi-center study will be conducted in two study facilities in Lucknow, Uttar Pradesh - Queen Mary Hospital (operated by King George's Medical University Lucknow) and Veerangana Avanti Bai District Women's Hospital. The selection of study sites was based on expected enrolment rates, feasibility of segregating the intervention and control mothers, and other pragmatic considerations.

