8.5. Randomisation, allocation and recruitment

This is an open-label individually randomised controlled study. The study biostatistician will generate a randomisation scheme with random permuted blocks of variable sizes between 2 to 6 using a computer program for each facility. The random allocation file for each facility will be electronically stored in the secure RedCap application database. During the enrolment process after securing informed written consent, the application will automatically assign the infant to the study group corresponding to the next sequence number and record the assigned group in the database, without making it visible in the case report forms. The study nursing team who will be conducting the screening and enrolment, will be able to access the study group assigned to enrolled infants. The study nursing team will also be responsible for overall strengthening of care in the study facilities, and will be referred to as the Screening, Enrolment and Systems Strengthening (SESS) team.

As an open-label trial, the SESS team, the intervention team (known as the 'KMC team'), and the participants will be aware of the assigned study group. However, special measures will be taken to reduce the risk of bias. The independent outcome assessment (IOA) team will be masked to the group allocation. The SESS team will ensure that a common minimum package of care is provided similarly to mother-baby dyads in both the study groups (please see section 8.7). Quality control measures will be adopted to ensure that the standard operating procedures are being duly followed and any deviation from the protocol will be documented. Measures to reduce the risk of bias will include standardised data collection in both the groups with well-defined monitoring and quality protocols.

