8.8. Outcomes, assessment and measurement

8.8.1. Primary outcome measures

	Primary Outcome Measures
Outcome 1: Percentage weight change over the first 48 hours after birth.	Description: Percentage weight change over the first 48 hours after birth is defined as:
	$\frac{Weight taken at (48 \pm 6) hours - Birth weight}{Birth weight} \times 100$
	All singleton infants will be weighed by workers trained and standardised in anthropometry assessments using a calibrated Seca 334 or equivalent digital weighing scale, accurate to ± 5 grams.
Outcome 2: The weight gain velocity during the newborn	Description: Weight gain velocity will be calculated as:
period	$\frac{Weight at ady n - Birth weight}{Birth weight} \times \frac{1}{n} \times 100$
	where n is the completed age of the baby at last follow-up, between 28-32 (included)
Outcome 3: Quality of	Description:
breastfeeding as measured through the Bristol Breastfeeding Assessment Tool (BBAT) score on Day 8 (i.e. at 7 completed days of	The BBAT assessment assigns numerical scores (0, 1, or 2) to four key breastfeeding components (position, attachment, sucking and swallowing) and summarising to a scale-score between 0-8, with a higher rating indicating better breastfeeding performance.
age).	The BBAT score is categorised into 3 categories: poor (0-2), moderate (3-6) and good (7-8).

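### The assessors described as masked also record skin-to-skin contact, and no rule separates this from the Day 8 scoring of the BBAT, a primary outcome, so its masking cannot be relied on as described

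*Protocol*

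**What the plan says.** Section 8.5 describes an open-label trial in which mothers, the enrolment team and the KMC team know the group. The stated counterweight is "The independent outcome assessment (IOA) team will be masked to the group allocation", and section 8.11 repeats it: "The IOA team responsible for conducting the data collection will be masked to the study group".

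Section 8.11 gives this team the follow-up visits, including "other care practices (24-hour recall questionnaire), etc". Its schedule lists, under outcome assessment, the item "F. Newborn Care Practices (SSC" on D1, D2, D4, D8, D15 and D29. The BBAT appears on D8 only. Section 8.12 confirms that the same team is standardised on the BBAT.

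Section 8.8.1 describes an observer rating: "The BBAT assessment assigns numerical scores (0, 1, or 2) to four key breastfeeding components (position, attachment, sucking and swallowing". Section 5.1.3 sets the hypothesis on dyads scoring below 7 out of 8.

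Section 8.6 defines the intervention as prolonged daily SSC over the first 72 hours, given bare-chested with a binder in the facility. After that, intervention mothers will "be advised to continue to breastfeed in the KMC position throughout the newborn period". Section 8.7 leaves SSC out of the thermal-care counselling given to both groups.

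**The concern.** What the assessor asks about in the SSC module is the treatment. A mother who reports many hours of SSC on D1, D2 or D4 has probably been counselled to give it, because the counselling common to both arms does not mention it. The D1 and D2 visits add what can be seen on the ward. On D8 the way the mother holds the infant is a further clue, and position is one of the four items scored.

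The BBAT is the primary outcome most open to an assessor's expectations. It is analysed at a cut, so one point from 6 to 7 moves a dyad from the unfavourable to the favourable category. If scoring leans even modestly towards the arm that the assessor believes she is seeing, the comparison is biased. No later analysis can restore masking that was lost when the score was given.

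**Working it through.** **Step 1: the masking statement against the schedule.**

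| Visit | SSC recall (Module F) | What the 24-hour recall covers | BBAT |
|---|---|---|---|
| D1 (24 h) | yes | 0–24 h, inside the 72 h intervention | no |
| D2 (48 h) | yes | 24–48 h, inside it | no |
| D4 | yes | if D4 means 3 completed days (72–96 h), starts between 48 and 72 h, so overlaps the third day wholly or partly | no |
| D8 (7 completed days, from 168 h) | yes | starts at 168 − 24 = 144 h or later, well after 72 h | yes |

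The D1, D2 and D4 answers are thus the revealing ones, and all three come before the BBAT. The D8 answer is weaker evidence of allocation, but it is collected at the BBAT visit itself.

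**Step 2: is there a separating rule?** The protocol names none: no separate BBAT assessor, no order of forms on D8, no bar on the D8 assessor having seen the dyad or its SSC data, and no check of masking. The measures it does name are standardised collection with monitoring and quality protocols (8.5) and spot checks of 10% of visits (8.12). The SSC log is a different item. It sits under intervention in the schedule, and section 8.15 gives KMC records to intervention staff. The point rests on Module F alone.

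**Step 3: the plan's own figures.** Section 8.9 uses a difference of 1.5, SD 3.6, two-sided 5%, 90% power and a design effect of 2.0:

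(1.960 + 1.282)² × 2 × 3.6² / 1.5² = 121.05, rounded up to 122; × 2.0 = 244 per group. With 5% loss, 122 / 0.95 = 128.4, so 129 per group per facility, and 4 × 129 = 516. Both figures reproduce.

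For the BBAT, 30% against 15% at 80% power:

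[1.960 × √(2 × 0.225 × 0.775) + 0.842 × √(0.30 × 0.70 + 0.15 × 0.85)]² / 0.15² = 120.5, so 121; × 2.0 = 242, which is within 244.

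**Step 4: what unmasked scoring could do (illustration).** The documents give no rate of up-scoring, so the fraction f is an assumption. Assume no true effect, with 30% of both arms truly below 7, and a fraction f of those in the intervention arm scored 7 or more. The observed proportions are p₁ = 0.30 and p₂ = 0.30 × (1 − f). With d = p₁ − p₂ and SE = √{[p₁(1 − p₁) + p₂(1 − p₂)] / n},

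P(p<0.05) = Φ(d/SE − 1.96) + Φ(−d/SE − 1.96).

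For f = 0.25 and n = 244: p₂ = 0.225, d = 0.075, SE = √(0.384375 / 244) = 0.0397, d/SE = 1.89, and P = Φ(−0.07) = 0.47.

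| f | p₂ | n = 244 per arm | n = 122 per arm (244 / 2.0) |
|---|---|---|---|
| 0.10 | 0.270 | 11% | 8% |
| 0.25 | 0.225 | 47% | 27% |
| 0.50 | 0.150 | 98% | 81% |

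A pooled standard error under the null changes no entry by more than about one percentage point. The last row is the planned effect itself: up-scoring half of the low dyads reproduces 30% against 15% with no treatment effect.

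**The case against.** A reader might infer that the masking cannot hold at all: that assessors have been told each mother's SSC practice before they score the BBAT, and that they visit groups kept physically apart. The documents do not support this.

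- They do not say that the D8 assessor has seen the dyad before. Nor do they say which of the paired assessors asks Module F; section 8.11 gives the breastfeeding observation to the woman and is silent on the SSC item.
- On D8 the schedule lists weight and the BBAT above Module F. Lettering is not an order of administration, but nothing shows that SSC is asked first.
- Segregation appears only as a reason for choosing sites: "feasibility of segregating the intervention and control mothers, and other pragmatic considerations". That mothers are in fact housed apart is an inference.
- Allocation is kept out of the case report forms. After 72 hours SSC is left to the mother's wishes, and feeding in the KMC position is advised only as far as possible. A D8 answer or posture is therefore a clue and not a disclosure, and control mothers may also give some SSC.
- Form order and rosters may sit in the SOPs (8.12) or the manual of operations (8.15), which are not at hand.
- The up-scoring rates are assumed, and so is their direction. The documents do not say how the KMC position scores on the position item.

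All of this stands as a limit on the claim. It does not remove the conflict between a plain statement of masking, made twice, and a schedule that has the same team ask about the intervention at every visit with no stated safeguard.

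**Conclusion.** The point holds in a limited form: masked BBAT assessment is not secured by the design and cannot be relied on as described. It is not shown that masking will fail for every dyad.

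The exposure is mainly the BBAT, one of three primary outcomes, with some for other assessor-rated or mother-reported outcomes. The two weight outcomes are read from a calibrated digital scale and are much less exposed. The sample size is not affected.

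The size is unknown. The 8% to 98% range is conditional on no true effect, a 30% control rate, bias towards the intervention only, and assumed up-scoring of 10% to 50%. The lower figure for each rate applies if the protocol's design effect is taken at face value. The conclusion itself rests on the masking statements and the schedule, not on these figures.

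**What to change.** 1. On D8, score and lock the BBAT before Module F or any other question about SSC.
2. Roster the female D8 assessor so that she has had no contact with that dyad on D1 to D4 and cannot see its earlier Module F data. Alternatively, give the SSC recall on D1, D2 and D4 to staff who do not score the BBAT. Moving D1 and D2 alone would leave D4 uncovered.
3. Record the assessor's guess of allocation straight after the BBAT, so that the loss of masking can be reported.
4. In sections 8.5 and 8.11, describe BBAT assessment as masking attempted, because the feeding position or the mother herself may still reveal the arm.

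The cost is less flexible rostering, plus form order and one added item. Existing teams can do this, with no change to endpoints or sample size. No change to where or how infants are weighed is asked for: the weights are little exposed, and moving dyads to a common weighing point would sit badly with section 8.6, under which routine care is given in SSC.
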